4.4 END OF STUDY DEFINITION

The end of the study is defined as the date when the last participant last visit (LPLV) occurs (includes the safety and follow-up visit), or the date at which the last data point from the last participant required for statistical analysis is received, whichever is the later date, unless the participant was prematurely discontinued.

5. STUDY POPULATION

The study population rationale is provided in Section [4.2.1](#).

The participants in this study will be healthy female and male volunteers and patients diagnosed with chronic HBV infection, between 18 and 65 years of age, inclusive, who fulfill all of the given inclusion criteria.

Prospective approval of protocol deviations from recruitment and enrollment criteria, also known as protocol waivers or exemptions, is not permitted.

5.1 INCLUSION CRITERIA

Participants are eligible to be included in the study only if all of the following criteria apply:

ALL STUDY PARTS

Informed Consent:

1. Able and willing to provide written informed consent and to comply with the study protocol according to ICH and local regulations.

Age:

2. Participant must be 18 to 65 years of age inclusive, at the time of signing the informed consent.

Weight:

3. Body weight of at least 45 kg and maximally 150 kg, and BMI within the range 18 to 32 kg/m² (inclusive).

Sex:

4. Male and female participants:

The contraception and abstinence requirements are intended to prevent exposure of an embryo to the study treatment. The reliability of sexual abstinence to meet enrolment eligibility needs to be evaluated in relation to the duration of the clinical study and the preferred and usual lifestyle of the participant. Periodic abstinence (e.g., calendar, ovulation, symptothermal, or post ovulation methods) and withdrawal are not acceptable methods of contraception.

- a) Female participants: Should be women of non-childbearing potential (WONCBP; see [Appendix 5](#)).

- b) Male participants: During the treatment period and for at least 105 days after the last dose of RO7239958 or placebo, agreement to:
- i. With partners who are women of childbearing potential (WOCBP): Remain abstinent (refrain from heterosexual intercourse) or use contraceptive measures such as a condom plus an additional contraceptive method that together result in a failure rate of < 1% per year.
 - ii. With pregnant female partners, remain abstinent (refrain from heterosexual intercourse) or use contraceptive measures such as a condom to avoid exposing the embryo.
 - iii. Refrain from donating sperm for at least 105 days after last dose of RO7239958 or placebo.

PART 1 (SAD HV) ONLY

Type of participants:

1. Healthy, as judged by the Investigator. Healthy status will be defined as the absence of evidence of any active or chronic disease following a detailed medical and surgical history, concomitant drug use (including hormonal supplements), a complete physical examination including vital signs, 12-lead ECG, hematology, blood chemistry, serology, and urinalysis.

Others Inclusions:

2. Non-smoker (nor tobacco containing products) for at least 90 days prior to dosing on Day 1, and agrees to remain non-smoker during the study.

PART 2 (CHB) ONLY

Type of Participants and Disease Characteristics

1. Positive serum HBsAg status for > 6 months prior to screening.
2. Serum HBsAg level ≥ 250 IU/mL at screening.
3. On stable entecavir or tenofovir (alone or in combination) treatment, and having received the same NUC in the 3 months prior to randomisation, and expected to remain on the same NUC for the duration of study participation.
4. HBV DNA below the lower limit of quantification (LLQ < 20 IU/mL) for ≥ 6 months prior to screening by local testing, and confirmed at screening.
5. Screening laboratory values (including hematology, chemistry, urinalysis) within normal ranges, or judged to be not clinically significant by the Investigator and Medical Monitor, and:
 - a) Screening alanine aminotransferase (ALT) and aspartate aminotransferase (AST) $\leq 2 \times$ upper limit of normal (ULN), confirmed between Day -7 to Day -4.

- b) Screening *gamma*-glutamyl transferase (GGT) \leq ULN (*Note: GGT \leq 1.5 x ULN is acceptable if considered not clinically significant*) and alkaline phosphatase (ALP) \leq ULN, and normal values of prothrombin time (PT), INR, and activated partial thromboplastin time (aPTT). *PT and/or aPTT $>$ ULN is acceptable if considered not clinically significant and INR and other parameters of liver function are within normal limits and there are no current and historical concerns. Whenever the Screening tests are repeated, the mean of the repeat values will be considered.*
 - c) Screening total bilirubin of \leq ULN (*Note: isolated bilirubin \leq 1.5 \times ULN is acceptable for patients with Gilbert's syndrome*).
 - d) Screening neutrophil count $>$ 1500 cells/mm³ (*Note: $>$ 1200 cells/mm³ is acceptable in participants of black race*).
 - e) Screening hemoglobin $>$ 11 g/dL in females and $>$ 12.5 g/dL in males.
 - f) Screening platelet count \geq 150,000 cells/ μ L.
6. No past or current diagnosis of cirrhosis. Transient elastography at screening showing a value consistent with a degree of liver fibrosis not higher than F3. By FibroScan, a cut-off of $<$ 8.5 kPa in the fasted status (last meal \geq 3 hours prior) is recommended.

5.2 EXCLUSION CRITERIA

Participants are excluded from the study if any of the following criteria apply:

ALL STUDY PARTS

Medical Conditions

1. Participants who have donated over 500 mL of blood or blood products or had significant blood loss within three months prior to screening.

PART 1 (SAD HV) ONLY:

Medical Conditions

1. History or presence of significant (as judged by the investigator) cardiovascular, respiratory, hepatic, renal, gastrointestinal, endocrine, haematological disorders, or diagnosed central or peripheral neurological disease, capable of significantly altering the absorption, metabolism, or elimination of drugs, of constituting a risk when taking the study treatment, or of interfering with the interpretation of the data.
2. Screening ECG showing clinically relevant abnormalities (including arrhythmias or marked QT abnormalities [QTcF $<$ 300 msec or $>$ 450 msec], or other cardiac abnormalities that are considered clinically significant by the Investigator. Known risk factors for Torsade de Pointes (e.g., hypokalemia, heart failure), or a personal or family history of congenital long QT syndrome.

3. Abnormal blood pressure: supine systolic blood pressure (SBP) <90 mmHg or >140mmHg or diastolic blood pressure (DBP) <45mmHg or >90mmHg at the time of screening and at Day -1, confirmed by two consecutive triplicate measurements, properly measured with well-maintained equipment.
4. History of lymphoma, leukaemia, or malignancy within the past five years, except for squamous epithelial carcinomas of the skin that have been resected with no evidence of metastatic disease for three years.
5. History or presence of liver disease, or known hepatic or biliary abnormalities (with the exception of Gilbert's syndrome or asymptomatic gallstones).
6. ALT $\geq 1.5 \times$ ULN at screening and at Day -1.
7. Any clinically significant out of range findings in other laboratory test results or any other clinically significant (as judged by the Investigator) abnormalities in the physical examination at screening and on Day -1.
8. Sensitivity to any of the study treatments, or components thereof, or drug or other allergy that, in the opinion of the Investigator, contraindicates the participation in the study.
9. Any clinically relevant history of hypersensitivity or allergic reactions, either spontaneous or following drug administration, or exposure to foods or environmental agents.
10. Any major illness within one month preceding the screening visit, or any febrile illness within the two weeks preceding the screening visit.
11. Concomitant disease or condition that could interfere with, or treatment of which might interfere with, the conduct of the study, or that would, in the opinion of the Investigator, pose an unacceptable risk to the participant in this study.

Prior/Concomitant Therapy

12. Used or intend to use of over-the-counter (OCT) or prescription medication (including herbal and traditional remedies) before study start and during the study as described in list of prohibited medications.
13. Live vaccine(s) within 28 days of screening, or plans to receive live vaccines during the study or within 28 days of the last dose.
14. Likely to need concomitant medication during the study period (including dental conditions).
15. Treatment with biologic agents (such as monoclonal antibodies, including marketed drugs) within three months or five half-lives (whichever is longer) prior to dosing.

Prior/Concurrent Clinical Study Experience

16. Currently enrolled in or have participated within the last 90 days or five times the half-life of the investigational drug (whichever is longer) from signing of consent in this or any other clinical study involving an investigational product or in any other type of medical research.
17. Exposure to more than four new chemical entities within 12 months prior to the first dosing day.

Diagnostic Assessments

18. Known positive for hepatitis B surface antigen (HBsAg or hepatitis B core total antibody [anti-HBc]) and/or hepatitis C, or positive HBsAg or hepatitis C virus (HCV) antibody test result at screening.
19. Known positive for human immunodeficiency virus (HIV) infection and/or positive for HIV infection at screening.
20. Positive pre-study drugs and alcohol screen.

Other Exclusions

21. History or evidence of alcohol abuse (consumption of more than two standard drinks per day on average; one standard drink equals 10 grams of alcohol), and/or drug abuse within one year of screening.
22. Any suspicion or history of substance abuse or dependence.
23. Dietary restrictions that would prohibit the consumption of standardised meal.
24. Healthy participants under judicial supervision, guardianship or curatorship.

PART 2 (CHB) ONLY

Medical Conditions

1. History or presence of significant (as judged by the Investigator) cardiovascular (including poorly controlled blood hypertension), respiratory, hepatic, renal, gastrointestinal, endocrine, haematological disorders, or diagnosed central or peripheral neurological disease, capable of altering the absorption, metabolism, or elimination of drugs, of constituting a risk when taking the study treatment, or of interfering with the interpretation of the data.
2. History or presence of bridging fibrosis or cirrhosis or decompensated liver disease.
3. History or presence of a medical condition associated with liver disease other than HBV infection (e.g., hemochromatosis, autoimmune hepatitis, alcoholic liver disease, toxin exposure, thalassemia, non-alcoholic steatohepatitis). Other known hepatic or biliary abnormalities (with the exception of Gilbert's syndrome or asymptomatic gallstones).
4. History of or suspicion of hepatocellular carcinoma or alpha fetoprotein (AFP) ≥ 13 ng/mL at screening.
5. History of lymphoma, leukaemia, or malignancy within the past five years, except for squamous epithelial carcinomas of the skin that have been resected with no evidence of metastatic disease for three years.
6. History of having received (in the last six months) or currently receiving any systemic anti-neoplastic (including radiation) or immune-modulatory treatment (including systemic corticosteroids).
7. History of organ transplantation.
8. Any major illness within one month preceding the screening visit, or any febrile illness within the two weeks preceding randomisation.

9. Clinically significant (multiple or severe) drug allergies, or intolerance to topical corticosteroids, or history of severe post-treatment hypersensitivity reactions (including, but not limited to, erythema multiforme major, linear IgA dermatosis, toxic epidermal necrolysis, or exfoliative dermatitis).
10. Estimated glomerular filtration rate (eGFR) < 70 mL/min/1.73m² (CKD-epi equation).
11. Confirmed QT interval corrected using Fridericia's formula (QTcF) >450 ms.
Patients with correctable risk factors for prolonged QT (e.g., electrolyte abnormalities) can be re-assessed after correction of the risk factor(s).

Prior/Concomitant Therapy

12. Live vaccine(s) within 28 days of screening, or plans to receive live vaccines during the study or within 28 days of the last dose.
13. Expected to need any other systemic antiviral therapy at any time during participation in the study, with the exception of current NUC treatment and / or oral/ topical therapy for Herpes Simplex Virus (HSV).

Prior/Concurrent Clinical Study Experience

14. Currently enrolled in (*i.e., the end of study visit has not been performed*) or have received *investigational treatment* within the last 90 days or five times the half-life of the investigational drug (whichever is longer) from signing of consent in this or any other clinical study involving an investigational product or in any other type of medical research, or the total volume of all blood samples provided during the follow-up visits of the former clinical trial exceeds 100 mL.

Diagnostic Assessments

15. Positive hepatitis C antibody at screening.
16. Known positive for human immunodeficiency virus (HIV) infection and/or positive for HIV infection at screening.
17. Positive pre-study treatment/alcohol screen.

Other Exclusions

18. History or evidence of alcohol abuse (consumption of more than two standard drinks per day on average; one standard drink equals 10 grams of alcohol) and/or drug abuse within one year of screening; positive test result for drugs of abuse at screening.
19. Patients under judicial supervision, guardianship or curatorship.
20. Sensitivity to any of the study treatments, or components thereof, or drug or other allergy that, in the opinion of the Investigator contraindicates the participation in the study.

5.3 LIFESTYLE CONSIDERATIONS

5.3.1 Meals and Dietary Restrictions

It is unlikely that food will have an impact on the PK of RO7239958; however RO7239958 doses will be administered in the fasted state (either two hours before or two hours after a meal). Taking RO7239958 in a fasted state will apply to healthy participants and CHB patients.

In CHB patients, any food restrictions applicable to NUCs should continue to be observed throughout the study.

In Part 1, participants must abstain from alcohol for 24 hours before the start of dosing until after collection of the final PK and PD sample. In Part 2, participants must abstain from alcohol abuse.

For Part 1, the use of tobacco products will not be allowed for at least 90 days prior to dosing on Day1 until after the final follow-up visit.

5.4 SCREEN FAILURES

Screen failures are defined as participants who consent to participate in the clinical study but are not subsequently randomized to study treatment. The Investigator will maintain a screening log to record details of all participants screened and to confirm eligibility or record reasons for screening failure. Individuals of Parts 1 and 2 who do not initially meet the criteria for participation in this study can be re-screened if deemed appropriate by the Investigator. Participants with borderline laboratory assessments can be re-tested within the assigned screening period or rescreened for the next cohort or arm.

5.5 RECRUITMENT PROCEDURES

Participants in Part 1 of the study might be identified for potential recruitment using pre-screening enrollment logs, clinical database and IEC/IRB approved newspaper/radio/social-media advertisements prior to consenting to participate in this study. *In Part 2, more participants than the minimum numbers may prove eligible throughout the screening process and to respect and recognize the participants' commitment, over-enrollment by a maximum of two patients per Arm will be accepted.*

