[REDACTED] Each cohort will implement sentinel dosing to monitor acute reactions over 24 hours post-dosing: Two participants will be dosed on Day 1, and at least one of the two participants will have received RO7239958; the remaining eight participants shall be dosed the following day (i.e., after 24 hours) following satisfactory clinical safety review of the first two participants by the Investigator. For each cohort, safety will be monitored for 28 days (21 days for safety assessment plus 7 days of clinical safety observation, before escalating to the next cohort. A dose escalation meeting will take place prior to starting the next cohort. In all participants, safety will be monitored for a total of 12 weeks post-dosing.

Part 2a – In Part 2a, CHB patients will be enrolled into one of two arms (Arms 1 and 2), which will run in parallel. Each arm will enroll seven participants using a 6:1 randomization scheme. To ensure balance between arms, enrolment of HBeAg positive participants will be capped. The Sponsor will communicate to the investigators the capping level arm prior to respective start of enrollment. Participants of each arm will receive RO7239958 or placebo over 4 weeks. [REDACTED]

[REDACTED]. Two additional, parallel arms (Arms 3 and 4) will open after Arms 1 and 2 have enrolled and followed-up for at least 28 days a sufficient number of participants to provide the safety and PK/PD information required to further inform dose and regimen optimization. An optional Arm 5 will open if further doses or regimens need to be explored based on data from Arms 3 and 4. A data review meeting will also take place before opening Arms 3 and 4 (and potentially optional Arm 5). Decision on dose levels and regimens for Arms 3 and 4 will be based on the safety, PK, and PD data from Arms 1 and 2 and all available safety and PK data from Part 1. If efficacious dose levels cannot be reliably predicted from PK/PD modeling and Part 1 data, the doses administered in Part 2a will be within the range demonstrated to be safe and well tolerated in Part 1. [REDACTED]

[REDACTED] In all patients, safety will be monitored for a total of 12 weeks post-dosing.

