Part 2b (optional) – The two additional arms (Arms 6 and 7) of Part 2b will open if further doses or regimens need to be explored based on the data from Part 2a, or a dose or regimen from Part 2a needs to be optimized and additional data evaluated. There may be inclusion of participants who are not treated with NUCs, or inclusion of a larger number of participants of a given HBeAg status. Each arm in Part 2b will comprise seven participants randomized to RO7239958 or placebo using a 6:1 randomization scheme. [REDACTED]

[REDACTED] In all patients, safety will be monitored for a total of 12 weeks post-dosing.

Treatment Groups and Duration

The IMPs are RO7239958 (active) and placebo. The dose given will be in milligrams per kilogram of body weight and administered SC.

Part 1: The total duration of the study for each participant will be up to 16 weeks, divided as follows:

- Screening: Up to 28 days
- In clinic period: Days -1 to 3.
- Treatment Period: Day 1
- Safety follow-up: up to at least 84 days after the dose of RO7239958 or placebo.

Part 2a: The total duration of the study for each participant will be up to 20 weeks divided as follows:

- Screening: Up to 28 days.
- In clinic period (optional): Days 1 to 3 and Days 29 to 30 (overnight stay optional).
- Treatment Period: Day 1 to 29.
- Safety follow-up: up to 84 days after the last dose of RO7239958 or placebo.

Part 2b: The total duration of the study for each participant will be up to 28 weeks divided as follows:

- Screening: Up to 28 days.
- In clinic period (optional): Days 1 to 3 and Days 29 to 30 (overnight stay optional).
- Treatment Period: Day 1 up to Day 85. Safety follow-up: up to 84 days after last dose of RO7239958 or placebo.

End of Study

The end of the study is defined as the date when the last participant last visit (LPLV) occurs (includes the safety and follow-up visit), or the date at which the last data point from the last participant required for statistical analysis is received, whichever is the later date, unless the participant was prematurely discontinued.

Data Monitoring: No

No Internal Data Monitoring Committee is planned for this study. A communication strategy will detail the data review and decision making prior to dose-escalation and initiation of study arms.

PARTICIPANT POPULATION

Participants will be healthy female and male volunteers and patients diagnosed with chronic HBV infection who fulfill all of the given inclusion criteria.

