14. Currently enrolled in (*i.e., the end of study visit has not been performed*) or have received *investigational treatment* within the last 90 days or five times the half-life of the investigational drug (whichever is longer) from signing of consent in this or any other clinical study involving an investigational product or in any other type of medical research, *or the total volume of all blood samples provided during the follow-up visits of the former clinical trial exceeds 100 mL.*

Diagnostic Assessments

15. Positive hepatitis C antibody at screening.
16. Known positive for human immunodeficiency virus (HIV) infection and/or positive for HIV infection at screening.
17. Positive pre-study treatment/alcohol screen.

Other Exclusions

18. History or evidence of alcohol abuse (consumption of more than two standard drinks per day on average; one standard drink equals 10 grams of alcohol) and/or drug abuse within one year of screening; positive test result for drugs of abuse at screening.
19. Patients under judicial supervision, guardianship or curatorship.

20. Sensitivity to any of the study treatments, or components thereof, or drug or other allergy that, in the opinion of the Investigator contraindicates the participation in the study.

NUMBER OF PARTICIPANTS

In Part 1, approximately 40-50 participants will be enrolled in four to five cohorts of 10 participants each (eight to receive RO7239958 and two to receive placebo). In Part 2, approximately 28-49 CHB patients will be enrolled in *four* to seven arms of seven participants each (six to receive RO7239958 and one to receive placebo). Part 2a will include approximately 28-35 participants in *four* to five arms. Part 2b will include approximately 14 participants in two arms.

CONCOMITANT MEDICATIONS

All medications (prescription and over-the-counter [OTC]) taken within 30 days of study screening until the follow-up visit will be recorded in the electronic case report form (eCRF).

For all parts of the study, paracetamol/acetaminophen, at doses of up to 1 g/day, is permitted for use any time during the study. Hormone replacement therapy (HRT) is allowed during the study.

As a general rule, no prescribed concomitant medication will be prohibited for Part 2 of the study. All concomitant medications (except standard NUC therapy) need to be discussed with the Medical Monitor prior to enrolling study participants.

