4.1.2 Dose Escalation Decision

The decision to escalate the dose in Part 1, and the decision to open Arms 3 and 4 in Part 2a (and potentially further arm(s) in *Part 2a and* Part 2b), will be made jointly by the Sponsor study team, the Investigator, and any other person the Investigator or the Sponsor consider necessary to assist with the decision (see Section 4.1.4). In Part 1, the decision will be made prior to each RO7239958 dose escalation following review of all relevant information, including applicable AEs, ECGs, vital signs, laboratory test results, and available PK data collected at the previous dose levels as applicable.

Dosing will be initiated in CHB patients in Part 2a with a safe dose as determined in Part 1, which will fall within the human efficacious dose range predicted with PK/PD modeling. The maximum dose in Part 2 will not exceed the maximum dose tested in Part 1 under any circumstances. Part 2a will only commence once all clinically relevant data are available from Cohort 4 of Part 1. Dose levels in Arms 3 and 4 of Part 2a will be based on all available PK and safety data from Part 1, and the safety, PK, and available PD data from Arms 1 and 2. Part 2a will employ real-time data analysis obtained during dosing and follow-up post-dosing. If data from Arms 1 and 2 are supportive, Arms 3 and 4 may start to enroll participants early, while follow-up post-dosing is ongoing in Arms 1 and 2. However, Arms 3 and 4 will only open once sufficient participants in Arms 1 and 2 have completed at least 28 days of post-dosing follow-up. *Arm 5 will be optional and will open if further doses or regimens need to be explored based on data from Arms 3 and 4.*

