9.2 SAMPLE SIZE DETERMINATION

The sample size was determined by practical considerations and not based on statistical power calculations. In Part 1, approximately 40-50 participants will be enrolled in four to five cohorts of 10 participants each (eight to receive RO7239958 and two to receive placebo). In Part 2, approximately 28-49 CHB patients will be enrolled in *four* to seven arms of seven participants each (six to receive RO7239958 and one to receive placebo). Part 2a will include approximately 28-35 participants in *four to* five arms. Part 2b will include approximately 14 participants in two arms.

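### Does the stated Part 2 sample size need correcting because Section 5.5 accepts up to two extra patients per arm?

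*Combined protocol and SAP*

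**What the plan says.** Section 9.2 states that "In Part 2, approximately 28-49 CHB patients will be enrolled in" four to seven arms, each with six patients on RO7239958 and one on placebo. It splits this into about 28-35 for Part 2a (four or five arms), and adds that "Part 2b will include approximately 14 participants in two arms". It also says that the size rests on practical considerations and not on power. The synopsis gives the same numbers.

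The design text in the synopsis and Section 4.1 agrees. For Part 2a, "Each arm will enroll seven participants using a 6:1 randomization scheme". For Part 2b, "Each arm in Part 2b will comprise seven participants randomized to RO7239958 or placebo using a 6:1 randomization scheme".

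Section 4.1.2 makes one Part 2a arm conditional: "Arm 5 will be optional and will open if further doses or regimens need to be explored". Part 2b as a whole is headed optional. Arms 1 to 4 are therefore the ones that are not optional.

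Section 5.5 treats the planned numbers as a floor. It notes that "more participants than the minimum numbers may prove eligible throughout the screening process" and, out of respect for those patients' commitment, that "over-enrollment by a maximum of two patients per Arm will be accepted".

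The Part 2 criteria in Section 4.1.3 are triggered by at least two, or for the more serious liver events at least one, of six patients receiving RO7239958.

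**The concern.** Section 9.2 and the synopsis are where a reader, including an ethics committee, looks for the number of patients to be exposed in this first-in-human study. Their totals are exact multiples of seven, so they contain no allowance for the extra patients that Section 5.5 permits. A reader would take 49 as roughly the most patients with chronic hepatitis B to be enrolled, and might fairly doubt that the word approximately stretches to 29% more.

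The stopping criteria raise a second doubt. If an arm has seven or eight patients on active drug, a criterion written for six does not say whether the number of events or their proportion governs. These criteria pause dosing in an arm, so any ambiguity in them deserves a check.

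**Working it through.** **Inputs.** Seven per arm, six active and one placebo (Section 9.2, synopsis). Four arms not optional, five in Part 2a with Arm 5, two in Part 2b, seven in all (Sections 4.1, 4.1.2, 9.2). At most two extra per arm (Section 5.5).

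**Step 1: reproduce the stated totals.** Arms × 7 gives 4 × 7 = 28, 5 × 7 = 35, 2 × 7 = 14 and 7 × 7 = 49. All four match Section 9.2 exactly, so it contains no arithmetic error.

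**Step 2: apply the allowance, before replacements.** Arms × (7 + 2):

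| Arms | Stated | Permitted ceiling | Excess |
|---|---|---|---|
| Arms 1-4 | 28 | 4 × 9 = 36 | 8 |
| Part 2a with Arm 5 | 35 | 5 × 9 = 45 | 10 |
| Part 2b | 14 | 2 × 9 = 18 | 4 |
| All seven arms | 49 | 7 × 9 = 63 | 14 |

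The relative excess is 9/7 − 1 = 28.6% in every row, and it requires every arm to over-enrol fully. With one extra per arm it is 8/7 − 1 = 14.3%, for example 4 × 8 = 32 against 28.

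**Step 3: active patients.** Section 5.5 does not say how the eighth and ninth patients are split. Assuming one or two of nine are on placebo, an arm has eight or seven active patients. Arms 1 to 4 together would then have 4 × 7 = 28 to 4 × 8 = 32, against 4 × 6 = 24 planned.

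**Step 4: does a larger arm weaken the stopping criteria?** Take the wording as a count. With n active patients and true event rate p, the chance of at least two events is 1 − (1 − p)^n − n·p·(1 − p)^(n−1). For n = 6 and p = 0.10 this is 1 − 0.5314 − 0.3543 = 0.1143. The rates below are assumptions, because the plan gives none.

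| Assumed rate | 6 active | 7 active | 8 active |
|---|---|---|---|
| 10% | 11.4% | 15.0% | 18.7% |
| 20% | 34.5% | 42.3% | 49.7% |
| 30% | 58.0% | 67.1% | 74.5% |

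For the at-least-one criterion the chance is 1 − (1 − p)^n, which at 10% gives 46.9%, 52.2% and 57.0%. Under a count, every criterion is met more readily as the arm grows.

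**Step 5: would any analysis change?** Table 11 in Section 9.3 defines the safety and efficacy populations by dosing, randomization and available assessments, not by a planned number. Extra patients who are dosed enter the summaries of their own arm, and placebo patients enter the pooled group for their part, with no new rule. Section 9.1 plans no hypothesis test, so no error rate or power depends on 28 or 49.

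**The case for a change.** The strongest case for a change is that Section 5.5 calls the planned number a minimum, whereas Section 9.2 presents it as the expected size. The stated ranges vary only with how many arms open, so nothing in them hints at nine per arm. One sentence would put this right. Parts of Section 4.1 and the synopsis design text are redacted and Figure 1 is not shown, but Section 9.2 and the participant numbers in the synopsis are readable and silent. All of that stands as a remark on presentation.

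It does not make 28-49 wrong. The protocol states both the plan and a bounded tolerance with its reason, so a reader of the whole protocol can find the limit. Nor is Section 9.2 a cap on exposure in any case: Sections 7.1 and 7.2 allow many discontinued or withdrawn patients to be replaced, so even the ceilings above would not be the maximum number treated.

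On the stopping criteria, the case is that two events are 33.3% of six but 25.0% of eight. If the proportion governed, three events would be needed in an arm of eight. At an assumed 10% rate the chance of meeting the criterion would then be 3.8%, against 11.4% for two of six. That would matter, but no passage states a proportional rule; the text asks for at least two or at least one. Safeguards that do not depend on arm size also remain: the discretionary criterion in Section 4.1.3, the halt in Section 6.6 and individual discontinuation under Section 7.1. The text is silent on larger arms, which falls short of contradicting Section 5.5.

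**Conclusion.** No change to the plan follows. The allowance in Section 5.5 is missing from Section 9.2 and the synopsis, and its ceiling is 28.6% above the stated size: 36 against 28 for Arms 1 to 4, and 63 against 49 if all seven arms open and fill completely. These figures exclude replacements. The stated size is an approximate plan for a descriptive, unpowered study, and no estimate, comparison or decision rests on it. A cross-reference would tidy the text without altering what the trial does or concludes.

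The criteria in Section 4.1.3 lack wording for an arm with more than six active patients. This rests on an assumed split of the extra patients and leads to a looser rule only under a proportional reading that the protocol does not state. It is a gap in detail that the sponsor may clarify when reconciling the two sections. No threshold is suggested here.
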